1.0 Objectives / Specific Aims

The purpose of this project is to determine the efficacy of POWER training for treating post-stroke depressive symptoms. We will also determine if depression limits response to rehabilitation and the extent to which changes in depression are associated with improvements in functional performance post-stroke. The PI and Co-I's have experience performing all of the proposed methodologies. Specifically, we have extensive experience implementing exercise programs in persons post-stroke;^{13,31,32,36} performing assessments of post-stroke walking;^{13,36} and diagnosing and treating depression.^{37,38,39,40}

Aim 1: Determine the efficacy of POWER training for treating PSD

We hypothesize significant reductions in HRSD scores in both groups, with improvements following POWER greater than control. We also expect greater response and remission rates in the POWER group.

Aim 2: Determine the influence of PSD on the rate and extent of response to POWER training

We posit that POWER training-induced improvements will be attenuated, though still significant, in depressed subjects. In addition, we hypothesize that improvements in walking speed and lower extremity muscle power generation will be contingent upon improvements in HRSD and that a critical threshold will determine the point at which depression is reduced thereby facilitating functional improvements.

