3.0 Intervention to be studied

Emerging evidence suggests that resistance training is effective at reducing depressive symptoms.^{11,12,27} We developed an innovative rehabilitation approach, Post-stroke Optimization of Walking using Explosive Resistance (POWER) training; a high-velocity, high-intensity lower extremity resistance training intervention that improves post-stroke muscular and locomotor function (RR&D RX000844).¹³ Preliminary findings from this study suggest POWER training reduces symptoms in those with mild to moderate depression (Figure 1). We seek to build upon these findings to determine its efficacy (vs. control) in treating PSD.

Chronic stroke survivors with mild to moderate depression (n=32) will be randomly assigned to the intervention (POWER) or attention control (stretching) group. POWER training will take place over a 12-week period (3 sessions/week) with exercises including leg press, calf raises, and jump training, all performed at high concentric velocity, as well as trials of fast walking. We will perform bi-weekly measurements of depressive severity using the Hamilton Rating Scale for Depression (HRSD).

Chronic stroke survivors with mild to moderate depression (n=16) as well as age (± 5 yrs), gender and severity-matched (determined by walking speed) non-depressed stroke subjects (n=16) will complete 12 weeks of POWER training. We will perform bi-weekly HRSD measurements as well as comprehensive dynamometric assessments of paretic and non-paretic knee extensor muscle power generation and self-selected walking speed at these same time points. Secondary assessments of locomotor function will be the six-minute walk test (6MWT) and the amount of community walking measured via step activity monitors (SAM).

Stretching is being used as an attention control condition for POWER training. Control subjects will participate in a stretching protocol for the same duration (i.e. 60 minutes per session) and frequency (3 days per week) for 12 weeks to ensure that they have equal interaction with the study staff and controlling for the effects of repeated social interaction on depressive symptoms.

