6.0 Number of Subjects

A total of 48 chronic stroke survivors will be accrued locally.

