Fatigue is defined as either voluntary exhaustion or inability to maintain a minimum cycling cadence of 40 RPM. Clinical criteria for termination include: 1) Hypertension: $\geq 220/120$ mmHg, or 2) Hypotension: a drop in diastolic blood pressure >20 mmHg, and O2 saturation $<85\%$. Electrocardiogram criteria include: 1) ≥ 1 mm horizontal or down sloping ST segment depression, 2) sustained paroxysmal ventricular tachycardia (>30 beats), and 3) sustained paroxysmal supraventricular tachycardia (>30 beats). If the test is terminated because of electrocardiographic findings, the subject will be managed medically as needed, referred for care, and disapproved for participation. Resting blood pressure and heart rate will be obtained prior to initiation of exercise as well as after the subject has been sitting on the stationary bicycle for 1 minute. During the exercise test, blood pressure readings will be obtained every 3 minutes. Heart rate will be obtained from the 12-lead EKG. Maximal heart rate will be recorded as the highest heart rate achieved during the exercise tolerance test.

Subject monitoring during testing and training: Blood pressure (BP) and heart rate (HR) will be monitored prior to, during, and at completion of each session. Subjects' resting diastolic BP must be <100 mmHg, systolic < 200 mmHg, and heart rate <110 beats/min to begin the testing.⁷⁴ Criteria for termination include subject complaints of shortness of breath, light-headedness, confusion, severe headache, or dyspnea; onset of angina; excessive blood pressure (systolic BP > 200 mm Hg, diastolic BP > 110 mm Hg), or drop in systolic BP > 10 mm Hg and inappropriate bradycardia (drop in heart rate > 15 bpm).

Experimental protocol for walking data collection: At the beginning of the first training session of every other week (bi-weekly), subjects will walk on a 10m. long gait mat (GaitRite) to measure self-selected and fastest comfortable walking speed and other spatiotemporal parameters. Subjects will be permitted a practice trial, and then be asked to complete three trials at each speed. For all trials, subjects will wear their own shoes and be asked to walk without an assistive device or ankle-foot orthosis. A safety harness mounted to the ceiling will protect the subject but will only support their body weight in the case of a loss of balance. A physical therapist will be present for all testing sessions as needed.

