12.0 Data Management

Data Analysis Plan: We will compare the effects of POWER training (vs. control) on HRSD scores. We will also determine response ($\geq 50\%$ reduction in symptoms) and remission ($\text{HRSD} < 10$) rates following training and at a six-month follow-up. We will utilize repeated measures mixed effects models to assess significant changes in outcomes between groups. Time and group will serve as dependent variables, as well as their interactions. A random intercept term will be included in the model to account for clustering within subjects. Various error structures associated with the repeated measures will be considered (e.g. compound symmetry vs. auto-regressive).

We will determine if PSD limits response to treatment by making between group comparisons of change (post-pre) in outcomes in depressed vs. non-depressed subjects utilizing repeated measures mixed models. Time (seven occasions), group (depressed vs. non-depressed) and their interaction will serve as dependent variables. Three primary dependent variables of interest here are, self-selected walking speed (SSWS) and paretic leg power generation. A random intercept term will be included in the model to account for clustering within subjects. Various error structures associated with the repeated measures over time will be considered (e.g. compound symmetry vs. auto-regressive). Analyses incorporating differences in outcomes as dependent variables will examine whether changes over time are more pronounced in depressed versus non-depressed subjects as well as whether changes are more pronounced in depressed subjects with the greatest improvement in HRSD. These models will also incorporate random subject effects to account for within-subject dependence. To determine associations between changes in outcomes, we will look at the relationships between outcomes using Pearson or Spearman correlations, depending on the distribution of the data. Further, we will use segmented (joint-point) regression to estimate if specific thresholds exist that mark in individual subjects where HRSD starts improving (decreases) and other outcomes start to improve (increase) to help us understand

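### One clause of Aim 2, that POWER training-induced gains remain significant in depressed subjects, cannot be supported by the Aim 2 analysis, because everyone in it receives POWER.

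*Combined protocol and SAP*

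**What the plan says.** All references are to the combined protocol and SAP.

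- **Hypothesis (Section 1.0, Aim 2).** "We posit that POWER training-induced improvements will be attenuated, though still significant, in depressed subjects". This makes two claims: the gain is smaller in depressed than in non-depressed subjects, and a gain caused by training is still present in the depressed.
- **Cohort (Section 3.0).** Sixteen depressed subjects are joined by "severity-matched (determined by walking speed) non-depressed stroke subjects (n=16) will complete 12 weeks of POWER training". Nobody in this comparison is untrained.
- **Model (Section 12.0, Data Analysis Plan).** Aim 2 is analysed by "making between group comparisons of change (post-pre) in outcomes in depressed vs. non-depressed subjects". The terms are listed thus: "Time (seven occasions), group (depressed vs. non-depressed) and their interaction will serve as dependent variables" (evidently meant as predictors). There is no treatment-arm term.
- **Randomised control (Section 3.0).** For Aim 1, 32 depressed subjects "will be randomly assigned to the intervention (POWER) or attention control (stretching) group". Section 12.0 names HRSD, response and remission for the POWER versus control comparison. Section 10.0 adds the paired associative stimulation (PAS) measures.
- **Walking speed (Section 10.0).** Every two weeks, "subjects will walk on a 10m. long gait mat (GaitRite) to measure self-selected and fastest comfortable walking speed". No arm is specified. Section 3.0, however, lists walking speed only in the paragraph on the all-POWER cohort.
- **Leg power (Section 10.0, Dynamometric Assessment).** Testing is described only for the period of POWER training.

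**The concern.** The null hypothesis behind the second claim is that POWER produces no functional gain in depressed subjects. The only related test the Aim 2 model can give is the time effect in the depressed POWER group, and its null is no change from baseline. Practice on a repeated walking test, contact with staff, or mood improving for other reasons would also reject that null.

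The plan's own hypotheses make this plausible. Aim 1 expects HRSD to fall in both randomised groups. Aim 2 makes gains in walking and leg power depend on improvement in HRSD. Together they allow walking to improve under stretching through mood alone.

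The trial could therefore report that depressed stroke survivors gain function because of POWER when the stretching arm had walked just as much faster. Randomised data that could separate the two may already be collected.

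**Working it through.** **1. The plan's own figure.** Section 12.0 gives 80% power for Aim 2 with n=26, a 0.13 m/s walking-speed difference (SD 0.2), a 17.88 ft/lb strength difference (SD 31.9) and AR(1) correlation 0.5. I read n=26 as 2 × 13. For the mean of m AR(1) measurements the variance factor is 0.260 (m=10) or 0.348 (m=7). Power = Φ(d / [SD·√factor·√(2/13)] − 1.96).

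- Strength, m=10: standard error 31.9 × √0.260 × √(2/13) = 6.38; 17.88/6.38 = 2.80; power 80.0%.
- Walking speed, m=7: standard error 0.2 × √0.348 × √(2/13) = 0.0462; 0.13/0.0462 = 2.81; power 80.3%.
- Walking speed at the stated m=10: power 90.1%.

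The 80% therefore fits a depressed versus non-depressed contrast, although walking speed matches only with the seven occasions of the Data Analysis Plan and not the ten in the sample-size text. Those two counts need reconciling. Reading n=26 as one pooled pre-post group fits less well (91% and 82%). Neither reading includes anyone without POWER.

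**2. What the within-group test does when POWER adds nothing.** Let the POWER-specific effect be zero and let both randomised arms share a gain g. The size of g is an assumption. Test week 12 minus baseline, two-sided 5% (sidedness is not stated). The non-centrality is g√n / SD of change, with n−1 degrees of freedom. Here n is 16 enrolled or 13 completers (Section 12.0).

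The plan does not say whether 0.2 m/s is the SD of change or of a single visit. If it is per visit with AR(1) 0.5 over seven occasions, the SD of change is 0.2 × √[2(1 − 0.5⁶)] = 0.28.

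| Assumed g (m/s) | SD 0.2, n=13 / 16 | SD 0.28, n=13 / 16 |
|---|---|---|
| 0.05 | 13.2% / 15.5% | 9.1% / 10.3% |
| 0.10 | 38.2% / 46.5% | 22.0% / 26.7% |

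Example: g=0.10, n=16, SD 0.2 gives non-centrality 0.10 × 4 / 0.2 = 2.0 against a critical t of 2.131, hence 46.5%. A smaller SD of change raises the rates: at 0.15 they are 20%/24% for g=0.05 and 60%/70% for g=0.10.

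**3. The two contrasts that remove g.** In the depressed versus non-depressed comparison, a gain equal in both groups cancels: (effect in depressed + g) − (effect in non-depressed + g). In POWER minus stretching, g also cancels, so under a zero POWER effect rejection stays at 5%.

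**4. Power of the between-arm test.** Non-centrality is d / [SD·√(2/n)], with 2n−2 degrees of freedom.

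| True difference (m/s) | SD 0.2, 13 / 16 per arm | SD 0.28, 13 / 16 per arm |
|---|---|---|
| 0.13 (plan's minimum difference) | 36% / 43% | 21% / 25% |
| 0.21 (pilot, 0.71 to 0.92) | 73% / 82% | 45% / 54% |

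The 95% CI half-width, t × SD × √(2/n), runs from 2.042 × 0.2 × √(2/16) = 0.14 m/s to 2.064 × 0.28 × √(2/13) = 0.23 m/s.

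**The case against.** **Aim 2 is about the influence of depression, and its analysis matches that.** This stands. The stated comparison and the reproduced power both concern depressed versus non-depressed subjects. Section 12.0 names no significance test within the depressed group; that test is inferred from a clause in the hypothesis. But without it the clause has no test at all, and the model offers no controlled one.

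**Other between-arm analyses are planned.** This stands in part. PAS is to be compared after POWER or control, and the Aim 1 paragraph of Section 12.0 speaks of changes in outcomes between groups. That phrase is generic and follows HRSD, response and remission, so it does not clearly commit to a walking-speed comparison. The accurate statement is that none is clearly specified, not that control data are used for HRSD alone.

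**The non-specific gain may be small.** This stands. Subjects are at least six months after stroke, a practice trial precedes gait testing, and the attention effect that the plan cites concerns depressive symptoms rather than walking. These features may reduce such a gain but cannot show it to be zero.

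**The remedy is weak.** This stands too. The 0.21 m/s benchmark comes from an uncontrolled pilot of twelve subjects, while Aim 2 itself expects smaller gains in depressed subjects. The stretching programme includes bridging and hip abduction, so it may affect leg function. Low power is a reason to lead with the interval. It does not make a before-after test answer the causal question.

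**Conclusion.** The clause claiming training-induced gains in depressed subjects goes beyond what the Aim 2 analysis can show. That follows from the design and does not depend on any number. The Aim 2 analysis set is not written out in Section 12.0; I take it to be POWER-only from Section 3.0 and from the n=26, and nothing contradicts this.

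The size is conditional. For an assumed shared gain of 0.05 to 0.10 m/s, with SD of change 0.2 to 0.28 m/s and 13 to 16 subjects, a false claim of benefit would arise in about 9% to 46.5% of trials.

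A reader might infer more than the documents support:

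- *That Aim 2 as a whole is uncontrolled.* The attenuation contrast is untouched by a non-specific gain equal in the two groups. It would be affected only if that gain differed by depression status.
- *That walking will improve without POWER.* The documents give no figure for this.
- *That a controlled analysis costs nothing.* Whether stretching subjects are walk-tested is unclear.

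The primary outcome, HRSD, is not affected.

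**What to change.** 1. Keep the depressed versus non-depressed interaction for the attenuation claim.
2. State whether stretching subjects do the bi-weekly gait-mat test. Section 10.0 suggests that they do; Section 3.0 leaves it open.
3. If they do, estimate the POWER minus stretching difference in self-selected walking-speed change from baseline to week 12 in the 32 randomised depressed subjects, using the mixed model planned for HRSD. Give the 95% CI as the main result and base any training-induced claim on it. Report the within-group change as descriptive.
4. If they do not, and in either case for leg power, report change during POWER training and drop the causal wording.

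**Cost.** With control walking data in hand, this is SAP wording and one further model, with no added patients or visits. Without such data, step 4 needs wording only; collecting them would add gait testing for 16 control subjects at sessions they already attend. The main drawback is that the claim becomes harder to make. By the normal approximation at SD 0.2, 80% power for 0.13 m/s needs 2 × (1.96 + 0.84)² × (0.2/0.13)², about 38 per arm, against the 16 planned.

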2.0 Background

With a surviving cohort of nearly 7 million individuals, stroke is the leading cause of long-term disability in the United States. Of the ~795,000 new strokes occurring in the U.S. each year, approximately two-thirds of survivors will have some degree of long term disability,¹⁸ and less than half will progress to independent community ambulation.¹⁹ Even among those who do achieve independent ambulation, significant residual deficits persist, with more than 60% of persons post-stroke reporting limitations in mobility related to walking.²⁰ Depression contributes directly to disability following stroke and is the single strongest predictor of quality of life. Importantly, improvement in depressive symptoms is associated with better functional recovery and return to activities of daily living. The prevalence of PSD coupled with the fact that returning to independent ambulation is the top priority for individuals in the first year post stroke²¹ necessitates development of effective rehabilitation strategies to reduce disability and improve quality of life for the millions of stroke survivors, their families and caregivers.

Post-stroke depression is common and treatment options are inadequate.

Post-stroke depression (PSD) is the most common neuropsychiatric consequence of stroke. Four out of five individuals develop major depressive disorder within seven years of stroke onset and point prevalence estimates for PSD are ~30%.³ Thus, more than 2 million individuals with PSD are presently living in the U.S. Current pharmacological treatments for depression in older individuals are generally ineffective (65-75% will not achieve remission) and often come at the cost of significant side effects (e.g. seizure, delirium and falls).^{6,22} Importantly, a review of treatment options for PSD found no evidence to support the routine use of drugs or psychological treatments for PSD⁵ and in a recent meta-analysis, 23 of 25 prospective studies that met the criteria for inclusion indicated that anti-depressant treatments were a significant predictor of prospective falls, independent of reduced physical

and cognitive function.²³ These issues highlight the need for alternative (non-drug) treatments with fewer side effects to successfully reduce PSD symptoms.

Individuals with PSD are largely ignored in rehabilitation research and limited data describe the effects of depression on rehabilitation outcomes.

Depression is reported to interfere with functional outcomes.⁷ Thus, clinical trials targeting recovery of walking have historically excluded depressed subjects.^{8,9,10} As such, there is an absence of data describing how individuals in this large clinical cohort respond to rehabilitation training. Given the prevalence of PSD, specific information regarding how depressive symptoms can be effectively reduced is a critical first step toward optimizing treatment approaches for these individuals. Further, data describing how depression impacts response to treatment would be extremely valuable to rehabilitation science and the development of effective treatments for PSD would have a major impact on healthcare delivery.

Resistance training can effectively improve post-stroke walking and emerging evidence supports its anti-depressant benefit

Hemiparesis, strictly defined as a muscular weakness or partial paralysis of half of the body, is seen in three-quarters of individuals post-stroke. A primary disability associated with post-stroke hemiparesis is the failure to make rapid graded adjustment of muscle force within the context of purposeful movement patterns, such as are required during walking. Progressive resistance training is widely accepted as the most effective method for developing muscular strength and is currently prescribed by most major health organizations for improving health and fitness.²⁴ Resistance training improves lower extremity strength following stroke and, when delivered at appropriate intensities, can provide significant functional benefit.^{25,26} In contrast, there exist studies in the post-stroke rehabilitation literature that report limited functional benefit of resistance type exercises, some of which fail to elicit significant gains in strength following this type of training.^{82,83,84} We recently developed an innovative rehabilitation approach, Post-stroke Optimization of Walking using Explosive Resistance (POWER) training (VA RR&D RX000844).^{13,31,32} A unique aspect of POWER training is the focus on high-intensity, high-velocity concentric and eccentric contractions to specifically target post-stroke deficits in muscle power generation. Interventions targeting muscle power (i.e. training at high-velocities) in the aged elicit an over two-fold greater improvement in peak power, when compared to slow velocity training, and explain more of the variability in functional performance.^{27,28,29} Data from our trial of POWER training show significant improvements in muscular and locomotor function¹³ and a recent pilot study suggest its potential to improve depression (see preliminary studies). The feasibility of resistance training to target depression has been shown in individuals following stroke and data from neurologically healthy subjects suggest the nature of POWER training may be key to its effectiveness for treating PSD.¹² Specifically, trials in older (non-stroke) subjects show benefits of resistance training on depressive symptoms and walking are dependent on training at high intensities, with reduced depression associated with improvements in muscle strength and function.¹¹ Similarly, high-intensity resistance training significantly improves depression in subjects at high risk for metabolic syndrome, with changes in depression correlated with change in muscle strength.²⁹

INNOVATION

Novel approach to treat PSD

The innovative approach proposed herein incorporates an extremely effective therapeutic intervention for post-stroke locomotor function that shows great potential as an anti-depressant treatment, the effectiveness of which could represent a major paradigm shift in post-stroke rehabilitation. Resistance training has shown potential to be an effective stand-alone treatment for non-stroke related depression, the efficacy of which is reportedly similar to antidepressant drugs.^{12,13,41} Follow-up studies show the effects of other forms of exercise persist longer and achieve higher rates of remission than pharmacological treatments. Thus, there is a sound rationale to investigate the influence of POWER training on post-stroke depression.

Conceptualizing depression as a state that limits neuroplasticity

Our conceptual framework considers that depression may be associated with disruption of homeostatic mechanisms that regulate neuroplasticity such that rehabilitation may not produce the same brain changes that it does in non-depressed individuals. The concept of impaired neuroplasticity in individuals with PSD is supported by findings of reduced synaptic plasticity in the motor¹⁷ and visual cortices¹⁶ as well as other telencephalic regions such as the hippocampus³⁰ in depressed patients. Together, these deficits suggest a deficiency in synaptic plasticity that is widespread, and not merely in the limbic and frontal regions that are most closely associated with depression. Although these findings have not been extended to PSD, conceptualizing depression as a disease which fundamentally limits plasticity allows us to pose specific questions regarding how depression limits response to rehabilitation, as well as how effective treatment of depression may improve rehabilitation outcomes. Thus, an extremely exciting possibility is that effective treatment for PSD may result in a virtuous cycle where reducing depression up-regulates neuroplastic responses, thereby facilitating functional gains. That is, effectively treating PSD may actually make an individual better able to recover from stroke.

The work proposed represents the first step in a longer line of investigation aimed at the development of appropriate therapeutic strategies to effectively ameliorate (attenuate) functionally limiting impairments in persons post-stroke. We believe that it will prove impossible to make substantial progress in patient-specific neurorehabilitation evaluation, treatment and outcomes without each being strongly based on a continually refined theoretical framework. Many contemporary neurorehabilitation strategies are based on assumed relationships between impairments of body structure & function, activity and participation; yet little evidence exists to define how these domains mechanistically relate to one another and the personal factors (e.g. depression) that may limit participation. The proposed studies would move this topic forward by elucidating the relationship between changes in depression and functional improvements following training as well as neuroplastic mechanisms of response to POWER training; thereby providing key data for future work to improve the *a priori* identification of fundamental barriers (and facilitators) to therapy.

Preliminary Studies for Aim 1:

POWER training is highly effective at improving post-stroke muscular and locomotor function: (*J Rehab Research & Development*. 52(1):77-84, 2015)

Twelve subjects (6–60 mos. post-stroke) participated in 24 training sessions of POWER training with exercises including leg press, calf raises, and jump training, all performed at high concentric velocity, as well as trials of fast walking. We measured self-selected walking speed as well as knee extensor and plantar flexor strength and power at pre-training, post-training, and at follow-up time points. Post-training improvements in lower

extremity muscle strength and power were accompanied by improvements in self-selected as well as fastest comfortable walking speeds. Specifically, strength increased by 25.0 and 23.3 percent in the paretic and non-paretic plantar flexor (PF) muscle groups, respectively. Improvements in knee extensor (KE) strength were not as large, with gains of 14.8 percent in the paretic side and 16.0 percent in the non-paretic side. Gains in KE peak power of 28.6 and 30.7 percent in the paretic and non-paretic limbs, respectively, were also found post-training. Self-selected walking speed increased from 0.71 to 0.92 m/s, exceeding the clinically meaningful difference reported for participants post-stroke. Fastest comfortable walking speed increased from 1.10 to 1.51 m/s.

POWER training improves depressive severity:

We have enrolled and trained 10 subjects to date with mild to moderate PSD in POWER training. We measured depression severity (HRSD), at pre-, mid- and post-training time points over the 12 week training period. HRSD scores prior to training (15.1 ± 7.5) decreased after 6 weeks (10.8 ± 4.3) and 12 weeks (8.5 ± 3.3) of training. In addition, 7 subjects realized a $>50\%$ reduction in depression severity (i.e. response) and 8 were considered to have achieved remission (i.e. HRSD < 10). Although we did not have a comparison group with PSD in this pilot study, these data suggest the potential for POWER training to positively impact depression severity in individuals with PSD.

